#### **7.4.1. Recording of concomitant medications/products and concomitant vaccination**

The following concomitant medications/products/vaccines must be recorded in the eCRF/CRF or the Expedited Adverse Event SAE/ADR Report if administered during the indicated recording period:

#### **7.4.2. Time window for recording concomitant medication/vaccination in the CRF**

- All concomitant medications, with the exception of vitamins and/or dietary supplements, administered at ANY time during the period starting with the administration of each dose of *Cervarix* and ending 30 days (~~Day 0 to Day 29~~) (**Day 1 to Day 30**) after each dose of *Cervarix* must be recorded in the CRF.
- Any vaccine not foreseen in the PMS protocol administered in the period beginning 30 days (~~Day 29 to Day 0~~) (**Day -29 to Day 1**) preceding each dose of *Cervarix* and ending 30 (~~Day 0 to Day 29~~) (**Day 1 to Day 30**) days after each dose of *Cervarix* must be recorded in the CRF.

**Section 8.2.3. Reporting adverse events of specific interest to GSK** has been removed as it has not been considered mandatory for PMS

#### **Section 8.2.3. Reporting adverse events of specific interest to GSK**

Several adverse events of specific interest including but not limited to potential immune mediated diseases (pIMD) and postural orthostatic tachycardia Syndrome (POTS), chronic regional pain syndrome (CRPS) following the *Cervarix* vaccination require close monitoring and further assessment. pIMD list is provided in-

## CONFIDENTIAL

208710 (EPI-HPV-077 VS KR PMS)  
Protocol Amendment 1 Final**Table 8 – List of pIMDs**

Neuroinflammatory disorders	Musculoskeletal disorders	Skin disorders

 
• Cranial nerve neuropathy, including paralysis and paresis (e.g. Bell's palsy).
 
• Optic neuritis.
 
• Multiple sclerosis.
 
• Transverse myelitis.
 
• Guillain-Barré syndrome, including Miller Fisher syndrome and other variants.
 
• Acute disseminated encephalomyelitis, including site specific variants e.g.: non-infectious encephalitis, encephalomyelitis, myelitis, myeloradiculoneuritis.
 
• Myasthenia gravis, including Lambert-Eaton myasthenic syndrome.
 
• Demyelinating peripheral neuropathies including: 
 
— Chronic inflammatory demyelinating polyneuropathy,
 
— Multifocal motor neuropathy
 
— Polyneuropathies associated with monoclonal gammopathy.
 
 
 
• Narcolepsy.
 
	
 
• Systemic lupus erythematosus and associated conditions
 
• Systemic sclerosis (Systemic sclerosis), including: 
 
— Diffuse Scleroderma
 
— CREST syndrome
 
 
 
• Idiopathic inflammatory myopathies, including: 
 
— Dermatomyositis
 
— Polymyositis
 
 
 
• Anti synthetase syndrome.
 
• Rheumatoid Arthritis and associated conditions including: 
 
— Juvenile Idiopathic Arthritis
 
— Still's disease.
 
 
 
• Polymyalgia rheumatica.
 
• Spondyloarthropathies, including: 
 
— Ankylosing Spondylitis,
 
— Reactive Arthritis (Reiter's Syndrome),
 
— Undifferentiated Spondyloarthritis,
 
— Psoriatic Arthritis,
 
— Enteropathic arthritis.
 
 
 
• Relapsing Polychondritis.
 
• Mixed Connective Tissue disorder.
 
• Gout
 
	
 
• Psoriasis.
 
• Vitiligo.
 
• Erythema nodosum.
 
• Autoimmune bullous skin diseases (including pemphigus, pemphigoid and dermatitis herpetiformis).
 
• Lichen planus.
 
• Sweet's syndrome.
 
• Localised Scleroderma (Morphea).
 

Vasculitis	Blood disorders	Others

 
• Large vessels vasculitis including: 
 
— Giant Cell Arteritis (Temporal Arteritis),
 
— Takayasu's Arteritis.
 
 
 
• Medium sized and/or small vessels vasculitis including: 
 
— Polyarteritis nodosa,
 
— Kawasaki's disease,
 
— Microscopic Polyangiitis,
 
— Wegener's Granulomatosis (granulomatosis with polyangiitis),
 
 
 
	
 
• Autoimmune hemolytic anemia.
 
• Autoimmune thrombocytopenia.
 
• Antiphospholipid syndrome.
 
• Pernicious anemia.
 
• Autoimmune aplastic anemia.
 
• Autoimmune neutropenia.
 
• Autoimmune pancytopenia.
 
	
 
• Autoimmune glomerulonephritis including: 
 
— IgA nephropathy,
 
— Glomerulonephritis rapidly progressive,
 
— Membranous glomerulonephritis,
 
— Membranoproliferative glomerulonephritis,
 
— Mesangioproliferative glomerulonephritis.
 
— Tubulointerstitial nephritis and uveitis syndrome.
 
 
 

**CONFIDENTIAL**208710 (EPI-HPV-077 VS KR PMS)  
Protocol Amendment 1 Final

Vasculitis	Blood disorders	Others

 
— Churg-Strauss syndrome (allergic granulomatous angiitis or eosinophilic granulomatosis with polyangiitis),
 
— Buerger's disease (thromboangiitis obliterans),
 
— Necrotizing vasculitis (cutaneous or systemic),
 
— anti-neutrophil cytoplasmic antibody (ANCA) positive vasculitis (type unspecified),
 
— Henoch-Schonlein purpura (IgA vasculitis),
 
— Behcet's syndrome,
 
— Leukocytoclastic vasculitis.
 
		
 
• Ocular autoimmune diseases including: 
 
— Autoimmune uveitis
 
— Autoimmune retinitis.
 
 
 
• Autoimmune myocarditis.
 
• Sarcoidosis.
 
• Stevens-Johnson syndrome.
 
• Sjögren's syndrome.
 
• Alopecia areata.
 
• Idiopathic pulmonary fibrosis.
 
• Goodpasture syndrome.
 
• Raynaud's phenomenon.
 

Liver disorders	Gastrointestinal disorders	Endocrine disorders

 
• Autoimmune hepatitis.
 
• Primary biliary cirrhosis.
 
• Primary sclerosing cholangitis.
 
• Autoimmune cholangitis.
 
	
 
• Inflammatory bowel disease, including: 
 
— Crohn's disease,
 
— Ulcerative colitis,
 
— Microscopic colitis,
 
— Ulcerative proctitis.
 
 
 
• Celiac disease.
 
• Autoimmune pancreatitis.
 
	
 
• Autoimmune thyroiditis (Hashimoto thyroiditis).
 
• Grave's or Basedow's disease.
 
• Diabetes mellitus type I.
 
• Addison's disease.
 
• Polyglandular autoimmune syndrome.
 
• Autoimmune hypophysitis.
 

If the subject develops adverse event of specific interest during the surveillance period, the physician shall report it as an AE and follow up the subject to collect information using Targeted Follow Up Questionnaires (TFUQ) provided by GSK. GSK may request additional information in such cases.

**CONFIDENTIAL**208710 (EPI-HPV-077 VS KR PMS)  
Protocol Amendment 1 Final

**Section 8. SAFETY** has been updated as it has been considered current PMS procedures and writing process as shown below:

### **8.3. Detecting and recording AEs, ADRs and SAEs**

The standard time period for collecting and recording SAEs will begin at the first receipt of Cervarix in the PMS and will end 30 days (~~Day 0 to Day 29~~)**(Day 1 to Day 30)** after the last dose (~~dose 1, 2 or 3~~) of Cervarix administered during the subject's participation in PMS. See Section 8.4 for instructions on reporting and recording SAEs.

An overview of the protocol-required reporting periods for AEs, ADRs and SAEs is given in Table 4.

All AEs reported within 30 days of each dose of the vaccine administered within the PMS and all SAEs reported throughout the PMS-PMS period up to 30 days (~~Day 0 to Day 29~~)**(Day 1 to Day 30)** after the last dose (~~dose 1, 2, 3~~) of Cervarix administered during the subject's participation in the PMS, ~~and received within the PMS~~ need to be recorded in the CRF. These AEs/ SAEs will be classified as expected/unexpected at the time of statistical analyses (refer to GLOSSARY OF TERMS for definitions of expected/unexpected adverse events).

All AEs reported during the 30 day (~~Day 0 to Day 29~~)**(Day 1 to Day 30)** follow-up period after each vaccine dose will be recorded using diary cards provided to the subjects or parent/LAR(s) of the subject. The AEs/SAEs will be analysed in the PMS report according to the expectedness and unexpectedness criteria as defined in the locally approved Prescribing Information (also refer to GLOSSARY OF TERMS).

#### **8.4.4. Completion and transmission of SAE reports to GSK Biologicals**

Facsimile (Fax) transmission *or e-mail delivery* of the SAE Report Form is the preferred method to transmit this information to the Contact for Reporting SAEs. In rare circumstances and due to failure of facsimile *or electronic* equipment, notification by telephone is acceptable, with a copy of the SAE Report Form sent by overnight mail. Initial notification via the telephone does not replace the need for the physician to complete and sign the SAE Report Form within 24 hours.

**CONFIDENTIAL**208710 (EPI-HPV-077 VS KR PMS)  
Protocol Amendment 1 Final

In the event of a death determined by the physician to be related to vaccination, sending of the fax **or e-mail** must be accompanied by telephone call to the PMS Contact for Reporting SAEs.

#### **8.4.5. Completion and transmission of non-serious AEs related to *Cervarix* reports to GSK**

Once a physician becomes aware that a non-serious AE related to vaccine has occurred in a PMS subject, the physician (or designee) must complete an ~~Expedited Adverse Event~~ **ADR** Report and forward it to GSK within 5 calendar days. The report will always be completed as thoroughly as possible with all available details of the event and then dated and signed by the physician (or designee). Even if the physician does not have all information regarding an AE, the report should still be completed and forwarded to GSK within 5 calendar days. Once additional relevant information is received, the report should be updated and forwarded to GSK within two weeks.

The physician will always provide an assessment of causality at the time of the initial report.

Fax transmission **or e-mail delivery** is the preferred method to forward the paper ~~Expedited Adverse Event~~ **ADR** Report to the PMS Contact for Reporting SAEs. In absence/ dysfunction of fax equipment **or electronic**, the PMS Contact for Reporting SAEs must be notified by telephone within 5 calendar days. As soon as the fax equipment **or electronic** is working again, the physician (or designee) must fax **or e-mail** the report to the PMS Contact for Reporting SAEs within 5 calendar days.

#### **8.4.6. Completion and transmission of pregnancy reports to GSK Biologicals**

Once the physician becomes aware that a subject is pregnant, the physician (or designee) must complete, date and sign a paper pregnancy notification report and fax **or e-mail** it to the PMS Contact for Reporting SAEs (refer to the local PMS contact information document) **WITHIN 2 WEEKS**.

### **8.5. Follow-up of AEs and SAEs**

All AEs documented at a previous visit/contact and designated as not recovered/not resolved or recovering/resolving will be reviewed at subsequent visits/contacts up to 30 days (~~Day 0 to Day 29~~) (**Day 1 to Day 30**) after the last dose (~~dose 1, 2 or 3~~) of *Cervarix* administered during the subject's participation in the PMS.

#### **8.5.1. Follow-up of pregnancies**

Pregnant subjects will be followed to determine the outcome of the pregnancy. At the end of the pregnancy, whether full-term or premature, information on the status of the mother and child will be forwarded to GSK Biologicals using the paper pregnancy follow-up report and the ~~Expedited Adverse Event~~ **SAE** Report if applicable. Generally, the follow-up period does not need to be longer than six to eight weeks after the estimated date of delivery.

**CONFIDENTIAL**208710 (EPI-HPV-077 VS KR PMS)  
Protocol Amendment 1 Final

**Section 10.2. Subject withdrawal** has been updated as it has been considered current PMS procedures as shown below:

### 10.2.1. Subject withdrawal from PMS

From an analysis perspective, a ‘withdrawal’ from the PMS refers to any subject who did not come back for the concluding visit/was not available for the concluding contact foreseen in the protocol.

All data collected until the date of withdrawal/last contact of the subject will be used for the analysis.

A subject is considered a ‘withdrawal’ from the PMS when no PMS procedure has occurred, no follow-up has been performed and no further information has been collected for this subject from the date of withdrawal/last contact.

Physicians will make ~~an attempt~~ **attempts** to contact those subjects who do not return for scheduled visits or follow-up.

Information relative to the withdrawal will be documented in the CRF. The physician will document whether the decision to withdraw a subject from the PMS was made by the subject’s parent(s) or LAR(s), or by the physician, as well as which of the following possible reasons was responsible for withdrawal:

- Serious adverse event.
- Non-serious adverse event.
- Protocol violation (specify).
- Consent withdrawal, not due to an adverse event.
- ~~Moved from the PMS area.~~
- Lost to follow-up.
- Death.
- Other (specify).

**Section 11. STATISTICAL METHODS** has been updated as it has been considered current PMS procedures as shown below:

### 11.1. Endpoints

- Occurrence of AEs during the 30-day ~~(Day 0 to Day 29)~~ **(Day 1 to Day 30)** follow-up period after each vaccine dose.
- Occurrence of SAEs reported throughout the PMS period up to 30 days ~~(Day 0 to Day 29)~~ **(Day 1 to Day 30)** after the last dose ~~(dose 1, 2 or 3)~~ administered during the subject’s participation in the PMS.

**CONFIDENTIAL**208710 (EPI-HPV-077 VS KR PMS)  
Protocol Amendment 1 Final**11.5. Statistical methods****11.5.2.1. Within group assessment**

The number and percentage, with exact 95% confidence interval (CI), of any AEs occurring within 30 days (~~Day 0 to Day 29~~)**(Day 1 to Day 30)** will be tabulated, for each dose, for overall doses and by number of subjects. The same calculations will be done for any adverse events according to the severity and for those assessed as causally related to vaccination.

The verbatim reports of signs and symptoms will be matched and coded according to the appropriate WHO-ART Preferred Term. The PMS physician will review and confirm the appropriate WHO-ART Preferred Term by responding to data queries if any discrepancies are reported while coding. The percentage of subjects with AEs occurring within 30 days (~~Day 0 to Day 29~~)**(Day 1 to Day 30)** with its exact 95% CI will be tabulated by preferred term. Similar tabulation will be done for AEs with relationship to vaccination and for AEs rated as grade 3.

The number and percentage of subjects who received concomitant medication/vaccination at least once during the 30-day (~~Day 0 to Day 29~~)**(Day 1 to Day 30)** follow-up period will be tabulated after each vaccine dose and overall, with exact 95% CI. Similar tabulations will be done for the number of subjects by types of medication/vaccination during the entire PMS period.

**11.5.1. Analysis of demographics/baseline characteristics** has been updated to address MFDS request for collection of information regarding medical history, physical examination, and concomitant medication as shown below:

Demographic characteristics (age, ~~weight~~, gender, and ethnicity) **and weight, height** of the PMS cohort will be tabulated using descriptive statistics. Mean, standard deviation, median, minimum and maximum will be calculated for continuous variables, and frequency and percentage will be calculated for categorical variables.

The medical history **by disease classification and per past/current status** and vaccination history of the vaccinated subjects will also be presented.

The distribution of subjects vaccinated among the PMS centres by years will be tabulated.

**Section 12. ADMINISTRATIVE MATTERS** has been updated as it has been considered current PMS procedures as shown below:

To comply with GEP, acceptable ethical principles, applicable local regulatory requirements, LSOP and administrative obligations relating to data collection, monitoring, archiving data, audits, confidentiality and publications must be fulfilled. ~~Blinding of subject initials when safety~~**Safety** data is used for analysis and ~~for GSK LOC to accurately provide the subject initials on the PMS report before submission to MFDS (Korea).~~ (GSK does not forward personally identifiable information. **In the PMS report, subject number which is a number identifying a subject will be reported to MFDS (Korea).** requires reporting of PMS subject's initials in the PMS report).

**CONFIDENTIAL**208710 (EPI-HPV-077 VS KR PMS)  
Protocol Amendment 1 Final

**12.6. Ownership, confidentiality and publication** has been updated in confidentiality section by referring to current Informed consents form (ICF).

**12.6.2. Confidentiality**

All information provided by GSK and all data and information generated by the site as part of the PMS (other than a subject's medical records) will be kept confidential by the physician and other site staff. This information and data will not be used by the physician or other site personnel for any purpose other than conducting the PMS. These restrictions do not apply to: (i) information which becomes publicly available through no fault of the physician or site staff; (ii) information which it is necessary to disclose in confidence to an IEC or IRB solely for the evaluation of the PMS; (iii) information which it is necessary to disclose in order to provide appropriate medical care to a PMS subject; **(iv) information from this PMS may also be combined with results from other research studies to learn more about the vaccine and related diseases;** or (v) PMS results which may be published as described in the next paragraph. If a written contract for the conduct of the PMS which includes confidentiality provisions inconsistent with this statement is executed, that contract's confidentiality provisions shall apply rather than this statement.

2.1 Study Objective

To assess the safety of GSK Biologicals' HPV vaccine containing HPV-16/18 L1 virus-like particles (VLPs) and AS04 adjuvant, in terms of frequency and intensity of adverse events (AEs) and serious adverse events (SAEs) when administered according to the local Prescribing Information (PI).

2.2 Number of Subjects

According to Ministry of Food and Drug Safety (MFDS) (Korea) regulation requirement, at least 600 evaluable subjects will be recruited for the post-marketing surveillance (PMS). Therefore, 660 subjects are expected to be enrolled through the PMS period considering a dropout rate of 10% (out of 600 subjects). Depending on the status of enrollment, the plan can be adjusted.

2.3 Study Period

The intended duration of this study is approximately 4 years.

2.4 Study Method

This prospective, observational PMS will be conducted at multiple centres in private clinics and hospitals (department of pediatrics and obstetrics & gynecology, etc.) in Korea for a period of 4 years.

3. Sequence of Planned Analyses

According to the standard for re-examination of new drugs, etc.(2012), the points to be reported are defined as follows (Chapter 3, item 1).

B. The regulation requires that periodical interim reports should be submitted to MFDS bi-annually for the first 2 years and annually for the remaining follow-up years. A comprehensive analysis will be performed at the end of the PMS. Regulatory post-marketing surveillance or special investigation results, which can be submitted to the MFDS (Korea) head within 2 months after the expiration of the investigation period.

According to the above, the analysis will be performed at the time of the second half of 2nd year period, end of 3rd year period and re-examination report.

However, statistical analysis may not proceed in the following cases.

- If report for non-execution is written due to no subject
- If case-report is written when the number of enrolled subject is less than 10 ^a

^a This criterion can be changed in accordance with GSK's request.

4. Analysis Sets (Study Cohorts)

This study set up the analysis sets for the safety analysis set (section 4.1) and non-safety analysis set (section 4.2). All analysis sets are based on all vaccination subjects who receive at least one dose of Cervarix (Total vaccinated cohort).

4.1 Safety Analysis Set (Total Safety cohort)

In standard for re-examination of new drugs, etc.(2012), the point to reported is defined as follow. (Chapter II, no 3).

2) Patient Population for Surveillance

A) Patients planned to receive a drug under surveillance by investigator's medical judgment shall be defined as a subject.

- B) Subject who do not use within approved range shall not be included in the safety analysis set in principal.
- ※ However, if data of subject whose use is beyond approved range is collected, perform analysis as a separate item.
- C) How to actually select subjects shall be described in detail.

The definition of the safety analysis set to this study is as follows.

Subjects who have been completed 30-days follow-up after at least once vaccinated Cervarix, will be included in the safety analysis set.

The below cases shall be excluded from the safety analysis set in the following order.

- (1) Subject who consented prior to the site initiation date
- (2) Subject who completed administration of Cervarix prior to the site initiation date
- (3) Subject who completed administration of Cervarix prior to the consent date
- (4) Subject who did not receive Cervarix
- (5) Follow-up failure: Subject for whom adverse event status (Adverse events status is unknown or missing) could not be established
- (6) Subject who has been violated the inclusion/exclusion criteria

[Inclusion criteria]

- Subject or/and subjects whose parent(s)/Legally Acceptable Representative(s) [LAR(s)], in the opinion of the investigator, can and will comply with the requirements of the protocol (e.g., complete the diary cards, return for follow-up visits).
- Korean male or female subjects aged 9-25 years who are eligible for the series of Cervarix according to the locally approved PI.
- Written informed consent obtained from the subject/from the parent(s)/LAR of the subject.

[Exclusion criteria]

- At the time of PMS entry, the contraindications and precautions of use indicated in the locally approved PI. PI should be checked and the subject must not be included in the PMS if there is any contraindication.
- Subjects who had previous administration of a HPV vaccine other than Cervarix will not be enrolled into the study.
- Subjects who are not eligible for vaccination with Cervarix according to the medical judgement of physician

- Child in care.
- (7) Subject who has been violated the dosage
- [Dosage]
- Receive 0.5mL dose by intramuscular injection
 - The 9-14 years old subjects can be vaccinated with 2 doses, 0 and 6-12 months schedule or with 3 doses, 0, 1 and 6 months schedule.
 - The 15-25 years old subjects should be vaccinated with 3 doses (0.5 mL each), 0, 1 and 6 months schedule.
 - In the 2-dose schedule, if the second dose is administered before 5 months after the first dose, the third dose vaccination is required. In the 3 doses schedule, if the vaccination schedule requires flexibility, the second dose can be administered between 1 and 2.5 months and the third dose can be administered between 5 and 12 months after the first dose.

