#### **8.5. Follow-up of AEs and SAEs (Amended: 14 May 2018)**

After the initial AE/SAE report, the physician is required to proactively follow each subject and provide further information to GSK Biologicals on the subject's condition.

All SAEs documented at a previous visit/contact and designated as not recovered/not resolved or recovering/resolving will be reviewed at subsequent visits/contacts until the end of the PMS.

All AEs documented at a previous visit/contact and designated as not recovered/not resolved or recovering/resolving will be reviewed at subsequent visits/contacts up to 30 days (**Day 1 to Day 30**) after the last dose of *Cervarix* administered during the subject's participation in the PMS.

Physicians will follow-up subjects:

- With SAEs or subjects withdrawn from the PMS as a result of an AE, until the event has resolved, subsided, stabilised, disappeared, or until the event is otherwise explained, or the subject is lost to follow-up.
- Or, in the case of other non-serious AEs, until or they are lost to follow-up.

Clinically significant laboratory abnormalities will be followed up until they have returned to normal, or a satisfactory explanation has been provided. Additional information (including but not limited to laboratory results) relative to the subsequent course of such abnormalities noted for any subject must be made available to the PMS Monitor.

GSK Biologicals may request that the physician perform or arrange for the conduct of additional clinical examinations/tests and/or evaluations to elucidate as fully as possible the nature and/or causality of the AE or SAE. The physician is obliged to assist. If a subject dies during participation in the PMS or during a recognised follow-up period, GSK Biologicals will be provided with a copy of any available post-mortem findings, including histopathology.

**CONFIDENTIAL**208710 (EPI-HPV-077 VS KR PMS)  
Protocol Amendment 1 Final

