### **10.2. Subject withdrawal (Amended: 14 May 2018)**

Subjects who are withdrawn because of SAEs/AEs must be clearly distinguished from subjects who are withdrawn for other reasons. Physicians will follow subjects who are withdrawn as result of a SAE/AE until resolution of the event (see Section 8.5).

Withdrawals will not be replaced.

**CONFIDENTIAL**208710 (EPI-HPV-077 VS KR PMS)  
Protocol Amendment 1 Final**10.2.1. Subject withdrawal from PMS**

From an analysis perspective, a ‘withdrawal’ from the PMS refers to any subject who did not come back for the concluding visit/was not available for the concluding contact foreseen in the protocol.

All data collected until the date of withdrawal/last contact of the subject will be used for the analysis.

A subject is considered a ‘withdrawal’ from the PMS when no PMS procedure has occurred, no follow-up has been performed and no further information has been collected for this subject from the date of withdrawal/last contact.

Physicians will make **attempts** to contact those subjects who do not return for scheduled visits or follow-up.

Information relative to the withdrawal will be documented in the CRF. The physician will document whether the decision to withdraw a subject from the PMS was made by the subject’s parent(s) or LAR(s), or by the physician, as well as which of the following possible reasons was responsible for withdrawal:

- Serious adverse event.
- Non-serious adverse event.
- Protocol violation (specify).
- Consent withdrawal, not due to an adverse event.
- Lost to follow-up.
- Death.
- Other (specify).

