### 11.3.2. Total Safety cohort

Safety analysis based on all vaccination groups will include all subjects who were vaccinated per product information and have completed 30-day follow-up after at least one dose, regardless of the number of dose.

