#### **11.5.2. Analysis of safety**

Safety analysis based on total vaccinated cohort, will include all subjects who were vaccinated per product information and have completed 30-day follow-up after at least one dose, regardless of the number of dose. Analysis of AE/SAE data reported after each dose will be performed separately.

**CONFIDENTIAL**208710 (EPI-HPV-077 VS KR PMS)  
Protocol Amendment 1 Final**11.5.2.1. Within group assessment**

The AEs/ SAEs will be analysed in the PMS report according to the expectedness and unexpectedness criteria. (Refer to **GLOSSARY OF TERMS** for the definitions of expected AEs and unexpected AEs).

The number and percentage, with exact 95% confidence interval (CI), of any AEs occurring within 30 days (**Day 1 to Day 30**) will be tabulated, for each dose, for overall doses and by number of subjects. The same calculations will be done for any adverse events according to the severity and for those assessed as causally related to vaccination.

The verbatim reports of signs and symptoms will be matched and coded according to the appropriate WHO-ART Preferred Term. The PMS physician will review and confirm the appropriate WHO-ART Preferred Term by responding to data queries if any discrepancies are reported while coding. The percentage of subjects with AEs occurring within 30 days (**Day 1 to Day 30**) with its exact 95% CI will be tabulated by preferred term. Similar tabulation will be done for AEs with relationship to vaccination and for AEs rated as grade 3.

The number and percentage of subjects who received concomitant medication/ vaccination at least once during the 30-day (**Day 1 to Day 30**) follow-up period will be tabulated after each vaccine dose and overall, with exact 95% CI. Similar tabulations will be done for the number of subjects by types of medication/ vaccination during the entire PMS period.

The outcome of pregnancy (reported in the pregnancy report form) for subjects who become pregnant subjects during PMS will be presented, If possible.

Serious adverse events and withdrawals due to adverse events reported during the PMS period (each subject receiving the vaccine up to 30 days after the last dose) will be described in detail.

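### The safety-set definition can be read two ways for an on-label subject with known AE status whose first 30-day window was cut short (minor)

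*SAP*

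**What the plan says.** **Who enters the main set.** SAP section 4 starts broadly: "All analysis sets are based on all vaccination subjects who receive at least one dose of Cervarix (Total vaccinated cohort". SAP 4.1 then narrows this: "Subjects who have been completed 30-days follow-up after at least once vaccinated Cervarix, will be included in the safety analysis set". The protocol has the same condition in 11.3.2 ("Safety analysis based on all vaccination groups will include all subjects who were vaccinated per product information and have completed 30-day follow-up") and in 11.5.2 ("Safety analysis based on total vaccinated cohort, will include all subjects who were vaccinated per product information and have completed 30-day follow-up"). The second of these names the total vaccinated cohort as its basis, although 11.3.1 gives that cohort no follow-up requirement.

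**Who is taken out.** SAP 4.1 lists seven exclusions. The only one about follow-up is item (5): "Follow-up failure: Subject for whom adverse event status (Adverse events status is unknown or missing) could not be established".

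**What happens to partial data.** Protocol 10.2.1 says: "All data collected until the date of withdrawal/last contact of the subject will be used for the analysis". It lists death, SAE and loss to follow-up among the reasons for withdrawal. The SAE endpoint in protocol 11.1 runs to 30 days after the last PMS dose and does not depend on completing a window.

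**Where excluded subjects go.** SAP 4.2 places them in the non-safety set, apart from the unvaccinated and those with unknown AE status. SAP 5.5 gives each set its own denominator. SAP 6.8.4 gives AE, ADR and SAE incidence and listings for the non-safety set, and introduces that analysis as covering use outside the approved range.

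**The concern.** The only objective is the frequency and intensity of AEs and SAEs, so membership of the main safety set fixes both numerator and denominator of the main result. If completing a window is a strict entry condition, an early death can remove its own subject from the main incidence. It also removes that subject from the SAP 6.8.2 tables by outcome, intensity and causality, which are run on the safety set only. If the exclusion list governs, the subject stays. Two analysts could therefore build different safety sets from the same text, and the difference would fall on the most serious events.

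**Working it through.** **The plan's own figures.** Enrolment is 600 × 1.10 = 660, as stated in protocol 11.2 and SAP 2.2. All eight rows of protocol Table 6 reproduce with Clopper-Pearson limits at n = 600: for example 6/600 gives 0.4 to 2.2% and 120/600 gives 16.9 to 23.4%. Neither figure is in dispute.

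**Test case against the text.** Take a subject who consents, receives a first PMS dose within approved use, has a reported SAE, and dies or is lost before that window closes.

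1. Entry sentence of SAP 4.1: no 30-day window was completed, so the subject is not admitted. No section says that death counts as completing the window.
2. Exclusions (1) to (3) concern the timing of consent, site initiation and dosing: they do not apply.
3. Exclusion (4), not vaccinated: does not apply.
4. Exclusion (5), AE status unknown or missing: does not apply, because an SAE is on record.
5. Exclusions (6) and (7), eligibility and dosage violations: do not apply. I take a single dose not to be a dosage violation, since the set is defined after one or more doses.

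So the entry sentence drops the subject and the exclusion list does not. SAP 6.1 reports reasons for membership of the non-safety set, but none of the listed reasons fits.

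**How wide the group is.** A subject who completed any earlier PMS window stays in on either reading. Protocol 8.5 also keeps following some subjects after an event ("With SAEs or subjects withdrawn from the PMS as a result of an AE, until the event has resolved, subsided, stabilised, disappeared"), so many of them may reach Day 30. What remains is mainly death, or an SAE and then loss, before any PMS window closes.

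**Size of the difference.** The documents give no SAE rate and no timing of dropouts, so the event counts below are assumptions. Assume 600 completers with no SAE among them. Limits are Clopper-Pearson: for x events in n, the lower limit is the 0.025 quantile of Beta(x, n − x + 1) and the upper limit is the 0.975 quantile of Beta(x + 1, n − x). For x = 0 the lower limit is 0 and the upper is 1 − 0.025^(1/n).

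| SAEs of this kind (assumed) | Entry sentence governs | Exclusion list governs, only these subjects added | Exclusion list governs, all 60 allowed-for dropouts kept |
|---|---|---|---|
| 1 | 0/600 = 0% (0 to 0.61%) | 1/601 = 0.17% (0.004 to 0.92%) | 1/660 = 0.15% (0.004 to 0.84%) |
| 3 | 0/600 = 0% (0 to 0.61%) | 3/603 = 0.50% (0.10 to 1.45%) | 3/660 = 0.45% (0.09 to 1.32%) |

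The last column is an extreme. It needs all 660 − 600 = 60 dropouts to be on-label, with known AE status, and to have left before any window closed.

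For any AE, assume 120/600 = 20% in completers and add 6 early leavers with known status. The result lies between 120/606 = 19.8% (none had an AE) and 126/606 = 20.8% (all did), so the direction is open.

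**A related mismatch.** SAP 6.8 runs the 6.8.1 summary on both sets. The table at the start of SAP section 6 limits the non-safety set to 6.8.4. So it is also unclear whether a subject in that set appears in the summary table.

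**The case against.** A coherent reading keeps the subject in. SAP 4.1 works through ordered exclusions, item (5) turns on whether AE status could be established, and a known SAE establishes it. That reading stands as one of two; it does not cancel the entry sentence, which states a condition the subject fails.

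A reader might infer three stronger things, which the documents do not support:

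- *That the SAE disappears, in breach of protocol 10.2.1.* That section names no analysis set or denominator. Even if the subject is dropped, SAP 6.8.4 gives incidence, exact limits and listings, and protocol 11.5.2.1 promises a detailed description: "Serious adverse events and withdrawals due to adverse events reported during the PMS period".
- *That the SAP departs from the protocol.* It repeats the condition in protocol 11.3.2 and 11.5.2. The tension lies inside the protocol as well.
- *That the subject would be labelled off-label.* The title of SAP 6.8.4 is neutral, and its set already includes subjects excluded for consent or site-initiation timing. Only the introductory sentence speaks of use outside the approved range. That sentence does not describe this subject, but it is not a label on the table.

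Rarity also counts. The subjects are aged 9 to 25 in routine vaccination, protocol 6.4.10 requires at least three telephone attempts for an unreturned diary, and the surveillance is descriptive.

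Finally, admitting early leavers can itself select on outcome: those with an event are more likely to have a known status than those who simply vanish. This stands, and it shapes the fix.

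**Conclusion.** The supported finding is an ambiguity, not a demonstrated loss of events. The entry rule and the exclusion list of SAP 4.1 disagree about a vaccinated, on-label subject with known AE status and an unfinished first window, and protocol 10.2.1, 11.1, 11.3.2 and 11.5.2 do not settle it. Each affected SAE moves the main incidence by about 0.17 percentage points, on the assumption of 600 completers without an SAE. How many such cases will occur cannot be derived from the documents, but the number is likely to be small. Severity: minor. It merits a correction because the cases at issue are the most serious ones and the correction is cheap.

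**What to change.** 1. Reconcile protocol 10.2.1, 11.3.2 and 11.5.2 with SAP 4.1 and 4.2. State that a subject given at least one PMS dose within approved use stays in the main safety set if AE status was established at any post-vaccination contact or report. This should apply whether or not there was an event, and the on-site observation alone should not count. Add that death or withdrawal before Day 30 does not by itself exclude.
2. Keep exclusion (5) for unknown or missing AE status.
3. Show the completers-only result as a sensitivity analysis.
4. In SAP 6.1, report the numbers with less than 30 days of follow-up and with unknown AE status. Note that early leavers with an event are more likely to have a known status, which can raise the incidence.
5. State whether the 600 evaluable subjects are counted on completers.
6. Make SAP 6.8 and the section 6 table agree on whether 6.8.1 is run on the non-safety set.

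The cost is wording in both documents and one extra table on data already collected. The drawback is that some subjects contribute less than 30 days, which items 3 and 4 make visible. The regulator's standard as excerpted in SAP 4.1 restricts the set to approved use and states no 30-day completion rule. The full text is not in the documents, so the sponsor should check the new definition against it.
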